3.0 Project Procedures

This will be a randomized pragmatic study for all patients ages 6-17 years with simple lacerations. Simple lacerations will be defined as lacerations within the scope of pediatric emergency medicine providers AND not requiring sedation or operative intervention. Subjects will be identified by the Emergency Department staff for enrollment. The goal number of enrolled participants will be 480, including 240 patients randomized into two groups, 120 per group, and 240 parents/guardians. The Emergency Department accepted to participate in this study and ED providers will complete the provider's survey. After signing the consent and assent form when appropriate, the patients will be randomized to either receive the standard of care or standard of care with immersive virtual reality goggles. Consent and assent will be obtained in the patient rooms within the emergency department. The standard of care shall be defined to include any of the following: local analgesia (topical LET and/ or subcutaneous lidocaine), oral or intranasal midazolam, distraction, Child Life Staff, or physical holding. Because each of the aforementioned interventions may vary between patients, it cannot be truly standardized; hence, this will be considered a pragmatic study. Patients randomized to the VR arm will receive the other standard procedures as well with VR goggles as an adjunct. Exclusion criteria include a history of epilepsy, visual or hearing impairment, or intellectual disability that would preclude use of VR goggles as determined by the guardian. Additionally, any lacerations around the eyes, eyebrows, and nose will be excluded as well as patients requiring sedation. Non-English speaking patients will be excluded as well. Hand lacerations will not be excluded.

Participants will be identified by ED staff following evaluation of the laceration. The ED staff will be given a flowchart with eligibility criteria. All interested participants who meet eligibility criteria will be consented. A research team member will obtain consent from parents or guardians by providing and reviewing the consent form (see Subject Consent Form). For patients who are between 8 and 17 years of age, a research team member will obtain assent by providing and reviewing the assent form (see Subject Assent Form). Consent and assent will be obtained in the patient's ED room.

Patients will be separated into groups age 6-11 and 12-17. Patients will be randomized via a selection of a sealed envelope which will contain instructions for use of the VR goggles. The goggles utilized will be Lenovo Mirage Solo with DayDream, which are standalone VR headset with WorldSense Body Tracking. Research staff will coach the child on age-appropriate games, as previously determined by Lenovo.

The goggles will be cleansed with Oxivir Tb disinfectant wipes after each use and allowed to dry in room air prior to next use. Education will be provided to all ED providers on the proper cleansing protocol for the VR goggles (Figure 4). The disinfectant protocol will be available for all users during the study, and has been approved by the director of Infection Control at Children's Hospital of the King's Daughters.

Following the laceration repair, the patient, guardian and health care provider will be surveyed (Figure 1, 2, and 3) on paper surveys. The survey includes Likert-type scale questions, binary

questions as well as incorporates the Wong Baker Faces Pain Scale and Children's Fear Scale. The duration of the procedure will be recorded by the healthcare provider who completed the laceration repair. Time of procedure will be defined as from the time of irrigation to wound dressing. Patients and parents will both be filling out their own individual surveys. The parent should complete the survey first before the child should the child need assistance with completion. Patients and parents may decline to participate in any survey at any time.

The recruitment period will be from November 2021 until February 2021. Enrolled participants will not be compensated, and enrollment will be completely voluntary.

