2.0 Objectives

The objective of this study is to determine if VR goggles can decrease patient pain and anxiety during simple laceration repairs. The primary outcome will be pain scores as assessed by the validated Wong Baker Faces Scale and anxiety scores as assessed by the validated Children's Fear Scale. A validated System Usability Scale (SUS) will be measured for each enrolled participant that used the VR goggles. Secondary outcomes include time of procedure, use of physical holding, adverse outcomes, and pharmacologic interventions.

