4.0 Statistical Analysis

Continuous variables will be presented as mean, standard deviation, median, 25th, and 75th percentile. Categorical variables will be presented as frequency and percentage. Generalized Linear Model (GLM) will be used to assess the effect of intervention on the outcomes of the surveys. The correlation between provider's, parent's, patient's survey will be analyzed using the Spearman's correlation test. All statistical tests will be performed using the R software. All statistical tests will be 2-sided and $p < 0.05$ will be considered as statistically significant.

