11. How would you rate the patient's pain:

Wong-Baker FACES® Pain Rating Scale

12. How would you rate the patient's fear:

No fear A little fear Some fear A lot of fear The most fear

Figure 3. Use of Immersive Virtual Reality for Laceration Repairs in the Pediatric Emergency
Department
Provider Survey

1. Procedure Duration (*from irrigation to closure end*):
A. <10 minutes
B. 10-15 minutes
C. 16-20 minutes
D. 21-25 minutes
E. >25 minutes

2. Did the patient use VR goggles for the procedure today?
 Yes
 No

3. Would you recommend VR goggles again for this procedure?
 Yes
 No

4. Did the patient need to be held during the procedure?
 Yes
 No

5. Did the patient receive medicine intended to help them stay calm?
 Yes
 No

6. During the procedure, did the patient experience any symptoms (select all that apply)?
 Did not experience any symptoms
 Dizziness
 Headache
 Nausea
 Vomiting
 Other (*describe below*)

7. How do you think the procedure went overall?
 Not well at all
 Somewhat not well
 Neutral
 Somewhat well
 Very well

8. In your opinion, did the virtual reality goggles make the procedure seem less scary to the patient?

Strongly disagree
 Disagree
 Neutral
 Agree
 Strongly agree

9. How would you rate the patient's pain:

10. How would you rate the patient's fear:

[figure not shown]

Figure 4. Education Plan for Disinfection Protocol for Virtual Reality Goggles

1. The company insert for cleansing the virtual reality goggles will be printed, laminated, and physically located with the goggles in their carrying case.
2. The protocol for cleaning will be addressed during an Emergency Medicine division meeting prior to the start of the project and detailed in the meeting minutes.
3. The protocol will be addressed during a pediatrics monthly resident meeting and dispersed in an email from the chief residents.
4. The protocol will be emailed to all rotating residents prior to the start of their rotation.
5. The protocol will also be disseminated to nursing staff and ED techs via [name] prior to the start of the project.
6. Research project staff will be available either in person or by phone to answer any questions regarding the disinfection protocol during the study phase of the project. Contact information will be included inside the carrying case for the goggles as well as on all written communications (division meeting minutes, chief email, etc.)

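### Expected need for holding and calming medicine is not recorded before allocation and the GLM names no baseline covariate, so precision on these two secondary outcomes is forgone

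*Combined protocol and SAP*

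**What the plan says.** Section 2.0 lists the outcomes at issue: "Secondary outcomes include time of procedure, use of physical holding, adverse outcomes, and pharmacologic interventions". Section 3.0 makes the same measures part of the background care: "The standard of care shall be defined to include any of the following", and the list that follows contains midazolam and holding. The VR arm keeps that list: "Patients randomized to the VR arm will receive the other standard procedures as well with VR goggles as an adjunct". No rule says when either measure is used, and the protocol gives this variability as its reason for calling the study pragmatic: "Because each of the aforementioned interventions may vary between patients, it cannot be truly standardized".

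Both outcomes come from the provider survey (Figure 3), completed after the repair. Item 4 is a yes/no question on holding. Item 5, the only survey item on medicines, reads "Did the patient receive medicine intended to help them stay calm". Neither asks for time, reason or prior intention. Item 2 of the same form asks about goggle use, so the provider knows the arm.

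Before allocation, staff assess the wound and apply the entry criteria: "The ED staff will be given a flowchart with eligibility criteria". Children who need sedation are excluded at that stage. Section 3.0 then separates children into ages 6-11 and 12-17 and has a sealed envelope drawn. Section 4.0 specifies a GLM for the survey outcomes, without a covariate or a link function.

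**The concern.** Whether a child is held or given a calming medicine probably depends heavily on how the child looked before the repair began. A clinician's view at that moment is a plausible predictor of both outcomes, and it is available before the envelope is opened. The plan neither records it nor names any other baseline variable for the model.

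Two things are lost. First, variation between children that a baseline covariate could explain stays in the error, so both comparisons are less precise than 240 children allow. Second, if by chance one arm receives more children who looked difficult, the report can show this only through indirect markers such as age. Neither loss can be repaired afterwards, because an expectation recalled once the arm and the course of the repair are known is no longer a baseline measurement.

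**Working it through.** **Inputs from the documents.** "240 patients randomized into two groups, 120 per group" (Section 3.0). "All statistical tests will be 2-sided", at the 0.05 level (Section 4.0). Two binary outcomes (Figure 3, items 4 and 5). No power, event rate or effect size supports the 240, so there is no figure of the plan's to reproduce.

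**Assumptions.** Rate 40% in control and 25% with VR; the prior judgement has sensitivity and specificity both equal to 60%, 70% or 80%.

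**1. Unadjusted power.** SE = √[(0.40×0.60 + 0.25×0.75)/120] = √(0.4275/120) = 0.0597. Then 0.15/0.0597 = 2.51, and Φ(2.51 − 1.96) = 0.71.

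**2. What the covariate explains (control arm).** At 80% accuracy, 0.4×0.8 + 0.6×0.2 = 44% are marked as expected. The event rate is 0.32/0.44 = 73% in those and 0.08/0.56 = 14% in the rest. At 60% accuracy, 48% are marked, with rates 0.24/0.48 = 50% and 0.16/0.52 = 31%.

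**3. Adjusted power.** Simulated logistic GLM, 1,500 trials per setting, common conditional odds ratio set so that the marginal VR rate is 25%:

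- accuracy 60%: 70% unadjusted, 72% adjusted
- accuracy 70%: 71% unadjusted, 75% adjusted
- accuracy 80%: 71% unadjusted, 85% adjusted

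Rejection with no effect was 4-6%. Repeat simulations gave 72-73%, 76-77% and 83-85% adjusted. The Monte Carlo standard error is about √(0.7×0.3/1500) = 1.2 points, so the gain at 60% accuracy is close to nil.

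**4. Cross-check on the risk-difference scale.** Assume a 30% rate in both arms. Unadjusted 95% half-width = 1.96×√(2×0.3×0.7/120) = 11.6 points. Adjustment multiplies it by √(1 − R²), where R² = [p(s − q)]²/[p(1 − p)q(1 − q)], q = ps + (1 − p)(1 − c), s is sensitivity and c is specificity.

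- s 60%, c 80%: q = 0.32, R² = 0.084²/(0.21×0.2176) = 0.154; half-width 10.7; 120/(1 − R²) = 142 per arm equivalent
- s 70%, c 85%: R² = 0.294; half-width 9.7; 170 per arm
- s 80%, c 90%: R² = 0.481; half-width 8.4; 231 per arm

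At a 20% rate, 10.1 points becomes 9.5, 8.8 or 7.6.

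**5. Chance imbalance.** With 44% marked, the difference between arms in that share lies within 1.96×√(2×0.44×0.56/120) = 12.6 points in 95% of trials. With no effect, each 10 points of imbalance moves the unadjusted outcome difference by 10×(0.73 − 0.14) = about 5.8 points at 80% accuracy, and by 10×(0.50 − 0.31) = about 1.9 points at 60%.

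**6. What adjustment does not do.** Suppose VR has no effect but staff omit 37.5% of uses because goggles are on: 0.40×(1 − 0.375) = 25%, the same marginal rates as above. At 80% accuracy the VR-arm rates by expectation become 0.73×0.625 = 45% and 0.14×0.625 = 9%. If VR truly spared 37.5% of these children, the table would be identical. In simulations of pure withholding at this accuracy, rejection was 66-72% unadjusted and 81-84% adjusted. At a 30% rate (sensitivity 70%, specificity 85%) with 25% of uses withheld, the mean difference was −7.5 points with or without adjustment, and rejection rose from 27% to 34%.

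**The case against.** A reader might infer that the missing record biases the comparison, or that adding it would expose decisions driven by the arm. The documents support neither. Randomisation balances expected need on average, so its absence creates no bias. As step 6 shows, a true effect and withholding can produce the same table of expected against actual use. Adjustment leaves any such bias in place and, on the risk-difference scale, narrows the interval around it. Telling the two apart would need information that the record does not supply, such as the time of and reason for each use. The documents also do not say who decides on holding or medicine, or whether medicine can be given before the envelope. In a pragmatic trial, the staff's response to goggles is arguably part of the strategy compared.

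A further objection is that useful covariates are already collected: age, developmental disability (guardian item 3) and previous stitches (guardian item 4). That is true, and imbalance in those can be examined. None of them is named in Section 4.0, however, and none measures expected need directly.

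Finally, the eligibility flowchart is not described as a per-patient data form, and its user need not be the person who does the repair. That stands, and it determines where the entry should be made.

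**Conclusion.** The point holds as a modest gain in precision on two secondary outcomes. Under 40% versus 25% with 120 per arm, power rises from about 70% to 72-85%. Under a 30% rate, the interval for the risk difference is 8-28% narrower. Both ranges rest on assumed rates and assumed accuracy of the prior judgement. The upper ends need a good predictor, and with a poor one the gain is negligible. No stated figure in the plan is wrong, and the primary outcomes are not affected. Interpretation of a lower rate in the VR arm remains limited by the unblinded, discretionary nature of both measures, with or without this change.

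**What to change.** Before the envelope is opened, the provider who will do the repair completes a short entry on a per-patient study form: expect to hold (yes/no), expect to give calming medicine (yes/no), and any calming medicine already given. The last item identifies medicine that preceded allocation, which the present survey cannot do.

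In Section 4.0, prespecify as covariates in the GLMs for holding and calming medicine:

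- the matching expectation
- age group (6-11, 12-17)
- previous stitches (guardian item 4), with a stated rule for unsure or missing answers

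State the link function as well, because under a logit link the adjusted odds ratio is conditional on the covariates and differs from the unadjusted one. Tabulate expected against actual use by arm as description only. State in the report that neither the table nor the adjustment separates a VR effect from staff holding back because of the goggles.

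The cost is one short form entry per child and a few sentences in Section 4.0. Writing down an expectation may anchor some providers, but it precedes allocation and so acts equally in both arms. The entry records intent only and changes no clinical rule.

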1.0 Background and Rationale

Small procedures are an everyday occurrence in the pediatric emergency department. Medical procedures often elicit anxiety, which amplifies the pain response.ⁱ Laceration repair is one of the most common procedures performed. Simple laceration repair can be challenging not from a technical standpoint, but due to patient cooperation secondary to patient pain and anxiety.ⁱⁱ Usually, uncooperative children squirm, kick, twist, and scream; this is physically challenging during a laceration repair. It is the norm for patients to require distraction, analgesia, and anxiolytics as well as physical holding in order to achieve adequate patient stillness for safe repair. Typical passive distraction methods include watching television, playing on a tablet or phone, parental engagement, or Child Life involvement. Distraction is an accessible, low-cost, and non-pharmacologic intervention.

Virtual reality is an evolving technology that allows a viewer to be immersed into a simulated environment using a head mounted device as well as hand-held controllers. Immersive virtual reality is an active form of distraction. Children who actively perform tasks or engage in activities forget about their pain and fear.ⁱⁱⁱ Virtual reality has been documented in the literature as a safe and effective tool to reduce both pain and anxiety surrounding painful procedures in pediatrics as a distraction technique.^{iv} It has also been theorized to diminish pain signals during painful procedures.^v This technology has been studied in burn scrubs,^{vi} wound dressing changes,^{vii} immunizations,^{viii} venipuncture,^{ix} lumbar punctures,^x and dental procedures^{xi} in pediatrics. However, virtual reality (VR) has not been well described for laceration repair in the pediatric emergency department setting. Side effects might include nausea, vomiting, motion sickness, but these have not been proven to be significant outcomes in the literature.^{xii}

In our emergency department, the standard of care involves topical lidocaine/epinephrine/tetracaine (LET) cream and/or subcutaneous lidocaine, positioning, Child Life staff, and distraction. For some children, oral or intranasal anxiolysis is necessary as well as physical holding. Our aim for this study is to determine if Virtual Reality goggles can improve patient pain and anxiety scores during simple laceration repair when compared to standard passive distraction techniques.

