5.0 Risks to Participants/ HIPAA Privacy Considerations

No personal identifiers will be recorded as part of the research study. Each enrolled participant will be given a unique number for data collection purposes. The risks involved in the study include adverse reactions to the VR goggles, which have been described to rarely cause nausea, vomiting, and motion sickness. There is a theoretical infection risk, but the VR goggles will be cleaned following a decontamination protocol following each use.

The data will be securely stored in RedCAP without any patient identifiers. The paper surveys will be kept in a locked drawer in a locked room within the Pediatric Department of Emergency Medicine offices.

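### The wound-site exclusion leaves scalp, ear and possibly forehead or temple lacerations eligible for a head-mounted device, with no stated check before randomisation that it can be worn

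*Combined protocol and SAP*

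**What the plan says.** Section 3.0 sets a broad entry rule: "This will be a randomized pragmatic study for all patients ages 6-17 years with simple lacerations". Simple lacerations are defined as "lacerations within the scope of pediatric emergency medicine providers AND not requiring sedation or operative intervention", which places no limit on body site.

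Two exclusions bear on the device:

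- By wound site: "any lacerations around the eyes, eyebrows, and nose will be excluded as well as patients requiring sedation". The only other statement about site goes the opposite way: "Hand lacerations will not be excluded".
- By ability to use the goggles: "a history of epilepsy, visual or hearing impairment, or intellectual disability that would preclude use of VR goggles as determined by the guardian".

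Section 1.0 describes the technology as one in which the viewer is "immersed into a simulated environment using a head mounted device as well as hand-held controllers". Section 3.0 names the model: "The goggles utilized will be Lenovo Mirage Solo with DayDream, which are standalone VR headset with WorldSense Body Tracking".

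The order of events in section 3.0 is that ED staff evaluate the wound and identify candidates with the help of a flowchart, interested families who meet the criteria go on to consent, and allocation by sealed envelope follows. No step asks whether the headset can be worn with the particular wound, and no rule covers a VR-arm child who cannot wear it. All three surveys (Figures 1 to 3) ask whether goggles were used. None asks for the wound site or the reason for non-use.

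**The concern.** Excluding wounds near the eyes, eyebrows and nose, and dealing expressly with hand wounds, suggests that the authors were thinking about interference between the wound and the device. That purpose is an inference, since the section gives no reason for the list. If it is right, the list covers only part of the area that a head-mounted device might touch or obstruct.

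A child with a scalp or ear wound meets every stated criterion. If that child draws the VR envelope and the headset cannot be worn, the child counts in the VR arm without receiving the intervention. Two things are at stake. The contrast between arms on both primary outcomes (pain and fear) is weakened by non-use that could have been foreseen at the bedside before allocation. And because neither wound site nor reason for non-use is recorded, the report could not say how much of the non-use arose this way.

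**Working it through.** **Which sites remain eligible.** Setting the criteria side by side:

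- Scalp and ear: not named in the site exclusion and not covered by the guardian-judged criterion. Eligible as written.
- Forehead, temple, upper cheek: depends on how far the undefined word 'around' extends. Wounds close to the eye or brow are plausibly out; an upper-forehead wound is probably in.
- Hand: expressly eligible.

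**The plan's own figure.** Section 3.0 states 240 patients, 120 per group. This cannot be reproduced, because no effect size, standard deviation, power or allowance for non-use is given. Working backwards with the normal approximation for two means, using two-sided alpha 0.05 (section 4.0) and an assumed 80% power:

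detectable difference = (1.960 + 0.842) × √(2/120) = 0.362 SD.

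**Dilution.** Let f be the share of enrolled children who cannot wear the headset because of the wound. Assume that they gain nothing from allocation to VR, that all wearers share the same effect d, that no control child uses goggles, and that patients are analysed as randomised. Then:

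- effect as randomised = (1 − f) × d
- equivalent number of patients = 240 × (1 − f)²
- patients per arm needed to restore power = 120 / (1 − f)²

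The documents give no value for f, so the rows below are illustrations. Power is for d = 0.362 SD with 120 per arm.

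| f (assumed) | Effect as randomised | Equivalent patients | Power | Per arm to restore |
|---|---|---|---|---|
| 0% | 0.362 SD | 240 | 80.0% | 120 |
| 5% | 0.344 SD | 217 | 75.9% | 133 |
| 10% | 0.326 SD | 194 | 71.3% | 149 |
| 20% | 0.289 SD | 154 | 61.1% | 188 |

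For example, at f = 10%, 240 × 0.9² = 194.4.

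f is the share unable to wear the headset, not the share with any head wound. Partial wear lowers it: if 10% of children had such wounds but each still obtained half the benefit, the average loss of effect would be 0.10 × 0.5 = 5%, which is the 5% row.

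**Excluding versus enlarging.** If a share f of currently eligible children were screened out, 240 / (1 − f) would have to be found to enrol 240: about 253, 267 or 300 at 5%, 10% or 20%. Keeping them in and enlarging the trial to recover the same power would take 2 × 133 = 266, 2 × 149 = 298 or 2 × 188 = 376 randomised children. Screening out is the cheaper route at each value.

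**The case against.** The strongest defence has four parts.

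1. *The written criteria may not be the whole screen.* ED staff work from a flowchart that is not in the documents, and the list in section 3.0 is not worded as exhaustive. A site or fit rule may already exist. This stands as a limit: a reader might infer that staff have no means of screening these wounds out, and the documents do not establish that. They show only that section 3.0 states no such rule.

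2. *The device's contact area is unknown.* The documents say that it is a head-mounted, standalone headset and describe no strap, pad or footprint. A wound under the headset is not the same as a headset that cannot be worn. This stands, and it is why f cannot be estimated.

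3. *A pragmatic trial may accept non-use.* Analysed as randomised, the smaller estimate is a valid effect of offering VR to the enrolled population, and use is recorded. This is correct: the loss is in power and in the size of the effect estimated, not in validity. But this non-use can be foreseen before allocation, and the forms would not reveal its cause.

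4. *Bias from dropping non-wearers or analysing by use has another source.* Section 4.0 names no analysis population, so that risk arises with any non-use, including refusal or nausea. It should not be charged to the site exclusion, and changing the exclusion would not cure it.

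A reader might also infer an added infection hazard from placing a shared device on an open wound. Section 5.0 says: "There is a theoretical infection risk, but the VR goggles will be cleaned following a decontamination protocol following each use". No text describes goggles being placed over a wound, and section 3.0 reports that the hospital's infection control director approved the cleaning procedure. The documents do not support that inference, and this point does not rely on it.

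**Conclusion.** The gap is real but modest, and worth closing because closing it is cheap. As written, section 3.0 lets scalp and ear wounds, and possibly forehead or temple wounds, be randomised to a head-mounted device with no stated check that it can be worn. That much rests on the text alone.

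The size is not known. The loss is nil if every such child can wear the headset. Under the assumptions listed, it amounts to the information of about 23 of 240 patients at f = 5% (240 − 217) and 86 at f = 20% (240 − 154). A reader might infer that the VR effect will certainly be diluted, or diluted heavily. The documents give neither the wound-site mix nor the share unable to wear the device, so they do not support that. Nor do they support saying that every forehead, temple or upper-cheek wound is eligible, since 'around' may already exclude some of them.

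**What to change.** In section 3.0, extend the site exclusion with: *or any laceration whose location would prevent wearing the headset or whose repair the headset would obstruct, as judged by ED staff before consent and before the envelope is opened*. This is a functional test, so it also settles the vagueness of 'around'. It is deliberately narrower than excluding every wound that the headset might touch, which would remove children who could still take part.

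Put the same line on the staff eligibility flowchart. If the flowchart already carries a site rule, reconcile the two so that the protocol and the bedside tool agree. On the provider form (Figure 3), add one item for wound site in both arms and one for the reason when a VR-arm child did not use the goggles.

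The cost is one clause, one flowchart line and two form items. ED staff already evaluate the wound before identifying a candidate, so no new step or personnel is needed. The downside is that some head wounds leave the recruitment pool, recruitment takes correspondingly longer, and the result does not apply to those wounds.

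### The surveys shown record neither wound site nor wound length, so the trial cannot describe the wounds, compare the arms on them, or adjust procedure time for them

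*Combined protocol and SAP*

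**What the plan says.** Eligibility (Section 3.0) is broad. A simple laceration is defined as "lacerations within the scope of pediatric emergency medicine providers AND not requiring sedation or operative intervention", with no limit on length. The one site restriction is that "any lacerations around the eyes, eyebrows, and nose will be excluded". The protocol adds that "Hand lacerations will not be excluded".

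Section 2.0 states: "Secondary outcomes include time of procedure, use of physical holding, adverse outcomes, and pharmacologic interventions".

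On data collection, Section 3.0 says that after the repair "the patient, guardian and health care provider will be surveyed (Figure 1, 2, and 3) on paper surveys". The provider survey (Figure 3) records duration in five bands, from under 10 to over 25 minutes, and asks "Did the patient need to be held during the procedure", answered yes or no. Section 5.0 says that each participant gets a study number and that the study keeps no personal identifiers.

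Section 4.0 names a generalized linear model (GLM) for the survey outcomes and lists no covariates.

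On the device, Section 1.0 describes virtual reality in general as "using a head mounted device as well as hand-held controllers". For the study headset, Section 3.0 says "Research staff will coach the child on age-appropriate games, as previously determined by Lenovo" and does not mention controllers.

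**The concern.** A long wound takes longer to irrigate and close than a short one, and site affects how awkward the repair is. With eligibility this open, length and site are likely to be strong predictors of procedure time. They are also known before allocation, which makes them natural baseline variables. If nobody writes them down, three things are lost:

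- The report cannot say what kinds of wound were treated.
- It cannot show whether the two arms received similar wounds.
- The model for procedure time cannot use them to reduce residual variance.

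Hand wounds deserve a marker of their own. The protocol singles them out for inclusion, and the rationale in Section 1.0 rests on active engagement. A reader will want to know how many there were and how they fared, and the planned data cannot answer.

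**Working it through.** **Check of the forms.** The surveys have 10 (patient), 12 (guardian) and 10 (provider) numbered items: 10 + 12 + 10 = 32.

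- Patient: age, earlier stitches, earlier and current VR use, willingness to use it again, symptoms, overall rating, whether VR made it less scary, pain, fear.
- Guardian: broadly the same topics, plus gender and developmental disability.
- Provider: duration band, VR use, VR recommendation, holding, calming medicine, symptoms, overall rating, whether VR made it less scary, pain, fear.

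None asks for wound site, length, suture count or hand involvement. The figures missing from the text sit at the pain and fear scales or among answer options, so they are unlikely to hide such an item. The eligibility flowchart in Section 3.0 is described as an aid for ED staff, not as a data form.

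**Plan's own figure.** The plan states no power, effect size or standard deviation, so there is nothing to reproduce beyond 2 x 120 = 240 patients. What follows is illustration, with 120 per arm taken from Section 3.0.

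**Chance difference in mean wound length**, in patient-level SDs:

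- Standard deviation of the between-arm difference: sqrt(2/120) = 0.129.
- 95% range: 1.96 x 0.129 = about +/-0.25.

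**What that does to procedure time.** If length and site explain a share R2 of the variance in time, the correlation is sqrt(R2). A one-standard-deviation chance difference then shifts time by 0.129 x sqrt(R2):

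- R2 = 0.10: 0.129 x 0.316 = 0.04 SD.
- R2 = 0.25: 0.129 x 0.50 = 0.065 SD.

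The unadjusted standard error already allows for shifts of this kind.

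**Precision gained by adjustment**, treating time as continuous, with R2 assumed:

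| R2 | SE factor sqrt(1 - R2) | SE reduction | Equivalent sample 1/(1 - R2) |
|---|---|---|---|
| 0.10 | 0.949 | 5% | 1.11 |
| 0.25 | 0.866 | 13% | 1.33 |

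The form records time in five bands, so the real gain would be somewhat smaller. The formula does not apply to holding, which is yes/no.

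**Hand wounds**, for assumed shares of 10% and 40%:

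- Patients: 240 x 0.10 = 24 and 240 x 0.40 = 96.
- 95% range of the between-arm difference in share, 1.96 x sqrt(2p(1 - p)/120): +/-7.6 and +/-12.4 percentage points.
- Difference detectable within the subgroup (two-sided 0.05, 80% power, continuous outcome), (1.960 + 0.842) x sqrt(2/(120p)): 1.14 and 0.57 SD.

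A hand-wound subgroup could therefore describe, but not test with any useful power.

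**The case against.** Covariate adjustment is optional in a randomised trial, the outcome concerned is secondary, and no statement in the plan is contradicted. All of that stands and keeps this a minor point.

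The surveys shown may also not be the whole data set. Section 2.0 promises a System Usability Scale that is not among the items in Figures 1-3, and the REDCap database is not reproduced. So the point can be made only about the surveys shown and the sources described. A reader might infer that site and length could never be recovered from the chart. The documents do not go that far. They describe no route, and Section 5.0 makes later linkage unlikely, but they do not rule out abstraction at enrolment.

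Three further readings are tempting and unsupported:

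- *Wound size biases the comparison.* It does not. Allocation is random, and chance imbalance is already reflected in the unadjusted standard error and p-value.
- *Hand wounds prevent full use of the intervention.* Controllers appear only in the general description of the technology in Section 1.0. The documents do not say that the study headset uses them or that a hand wound limits play, and a wound on one hand leaves the other free. Site alone would not show which children could use a controller, so it could not explain a null result.
- *Adjustment would sharpen the holding result by the same amount.* In a logistic model, adding covariates generally increases the standard error of the log odds ratio and changes the estimand to a conditional odds ratio.

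What survives is the core: a likely strong predictor of procedure time is not captured under the plan as written, and analysts cannot supply it afterwards by any described means.

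**Conclusion.** The concern holds in a limited form. On the surveys and data sources described, the trial cannot report wound length or site, check the arms for comparability on them, or use them to improve precision for procedure time. Validity of the randomised comparison is not in question.

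The size is modest: a standard error about 5-13% smaller for procedure time. This rests on an assumed 10-25% of variance explained, for which the documents give no anchor, and on treating time as continuous. No precision gain is claimed for holding. Hand wounds are worth identifying because the protocol expressly includes them, but only for description.

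**What to change.** 1. **Record.** Add one line to the existing wound evaluation, completed before the envelope is opened: laceration length in cm and body site (hand, other limb, head, trunk), so that hand yes/no can be read off. Carry it into the database under the study number.
2. **Report.** Show length and site by arm in the baseline table.
3. **Prespecify.** Add a sentence to Section 4.0 naming length and hand yes/no as covariates in the GLM for procedure time.
4. **Holding.** Treat any adjusted analysis as supportive and report it as a standardised risk difference.
5. **Hand wounds.** Give results for hand versus other wounds descriptively, with no test and no claim about the mechanism.

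The cost is a few seconds per patient and two model terms. Using the full four-level site variable would need four terms (one for length, three for site). No extra visit, staff or procedure is needed.
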